1.4. Schema

FC=Facilitation Call
*Interim Analysis will be conducted approximately after the 4th monthly facilitation call and interim interviews have been completed with site staff. Completed Month 4 surveys from patients will also be included.

1.5. Schedule of Activities (SoA)

There are additional PK assessments for any pregnant participants who are remaining in the study. See [Appendix 8](#)

Table 3 Schedule of Activities for Patient Study Participants (CAB LA + RPV LA Monthly Administration)

Procedures	Screening ^a	Intervention Period												WD ^o	
		Day 1	Month 1	Month 2	Month 3	Month 4	Month 5	Month 6	Month 7	Month 8	Month 9	Month 10 ^c	Month 11 ^c		Month 12 ^c
Written Informed Consent ^b	X														
Demography	X														
Eligibility Verification	X														
Physical Exam	X														
Medical History	X														
Center for Disease Control and Prevention (CDC) Classification	X														
Randomization for interviews		X													
Rapid Plasma Reagin (RPR)	X														

Procedures	Screening ^a	Intervention Period												WD ^o	
		Day 1	Month 1	Month 2	Month 3	Month 4	Month 5	Month 6	Month 7	Month 8	Month 9	Month 10 ^c	Month 11 ^c		Month 12 ^c
Symptom Directed Physical Exam and Medical Assessment ^d	X	X	X	X		X		X		X		X		X	X
Injection site reaction (ISR) assessment			X	X	X	X	X	X	X	X	X	X	X	X	X
Vital Signs (temperature, blood pressure [BP], heart rate [HR]) ^e	X	X	X	X		X		X			X			X	X
Weight, Height & body mass index (BMI) ^f	X	X	X					X						X	X
HIV Associated Conditions, AE and serious adverse event (SAE) Assessments & Con Meds	X	X	X	X		X		X		X		X		X	X
12-Lead ECG ^g	X														X

Procedures	Screening ^a	Intervention Period												WD ^o	
		Day 1	Month 1	Month 2	Month 3	Month 4	Month 5	Month 6	Month 7	Month 8	Month 9	Month 10 ^c	Month 11 ^c		Month 12 ^c
Clinical and Hematology			X	X		X		X			X			X	X
Pregnancy Testing (U)rine or (S)erum ^h	U	U	U	U	U	U	U	U	U	U	U	U	U	U	U
HIV-1 RNA	X	X	X	X		X		X		X		X		X	X
Plasma sample for storage ^{i,j}		X	X	X		X		X		X		X		X	X
CD4+cell counts	X	X	X	X		X		X			X			X	X
Urinalysis	X														X
Glucose	X														
Prothrombin time (PT)/ partial thromboplastin time (PTT)/ international normalized ratio (INR)	X														X
Oral study product dispensation		X													

Procedures	Screening ^a	Intervention Period													WD ^o
		Day 1	Month 1	Month 2	Month 3	Month 4	Month 5	Month 6	Month 7	Month 8	Month 9	Month 10 ^c	Month 11 ^c	Month 12 ^c	
LA study product administration ^k			X ⁿ	X	X	X	X	X	X	X	X	X	X	X	
Participant Visit Reminder Contact	X	X	X	X	X	X	X	X	X	X	X	X	X	X	
Participant Contact Detail Confirmation	X	X	X	X	X	X	X	X	X	X	X	X	X	X	
Record study visit length ^l			X				X						X		
Patient Questionnaire			X			X								X	
Selected Patient Interviews (SSI) ^m		X												X	

See footnote "c" for continuation of visit schedule after Month 12, if required. Subjects will continue on study until the CAB + RPV LA regimen is either locally approved and commercially available, the participant no longer derives clinical benefit or meets a protocol-defined reason for discontinuation or until development is terminated.

- A screening visit will be conducted within 21 days of Day 1. However, it is preferred for Day 1 to be conducted as soon as practical after all screening results are available.
- After discussion of risk:benefit, a pregnancy specific ICF addendum must be signed by pregnant participants who wish to remain in the study
- Continue this pattern for visits for the remainder of the study if needed, until commercial CAB + RPV LA is available. For example, Month 13 will be conducted as per Month 10, Month 14 will be conducted as per Month 11, Month 15 will be conducted as per Month 12, Month 16 will be conducted as per Month 10, and so on. The exception to this pattern is that no questionnaires, study visit length collection, or patient interviews will be conducted after the Month 12 visit.
- Physical exams should be conducted as part of normal routine clinical care but data will not be collected in the electronic case report form (eCRF). Medical assessments include any decisions the study staff must make for participant management.
- Measure vital signs after about 5 minutes of rest in a semi-supine position.

- f. Height collected at Day 1 only.
- g. At Screening, ECGs should be performed in triplicate at least 5 minutes apart and following 5 minutes of rest in a semi-supine position. ECG evaluations performed at subsequent visits should be obtained after dosing, preferably 2-4 hours post dosing. ECG at Withdrawal should be performed following 5 minutes of rest in a semi-supine position.
- h. A (-) urine pregnancy test is required prior to any injection and as required by medical monitor after a treatment interruption. A (+) urine test should be confirmed with a stat serum test. A Serum pregnancy test should be performed at any time pregnancy is suspected by the Investigator and may be used in place of a urine test at the discretion of the investigator. Pregnant participants who remain in the study do not need pregnancy testing during the study, for the duration of their pregnancy. Pregnant participants remaining in the study have additional assessments required, as described in [Appendix 8](#)
- i. Plasma for storage samples are collected for possible future analyses, back-up in cases of loss/damage in transit, geno/pheno analyses for virologic failures or PK in the event of maladministration or virologic failure.
- j. Participants who get pregnant while in study will have additional PK samples for CAB and RPV obtained. See [Appendix 8](#)
- k. Monthly injections are 1 x CAB LA 600 mg IM + 1 x RPV LA 900 mg IM at Month 1. Subsequent injections beginning at Month 2 are 1 x CAB LA 400 mg IM + 1 x RPV LA 600 mg IM. If possible, injections should be spaced approximately 2 cm from one another and from the site of any previous injection and/or any injection site reaction. Bring RPV LA to approximately room temperature prior to injecting. Time and location of injection (right or left) as well as needle length used will be collected in the eCRF. **IM dosing is expected to occur during the month in which the participant's projected visit falls (as according to the Day 1 visit). A dosing window of +0 / -7 days from date of projected visit is stipulated for IM dosing at Month 2 and Month 3. A (+ or -) 7 day window from date of projected visit is stipulated for IM dosing beginning at Month 4. All decisions regarding dose interruption/resumption must be discussed with the medical monitor in advance.**
- l. Length of study visit from arrival until departure from clinic will be evaluated. Time of arrival, time of appointment, and departure times will be recorded in the eCRF.
- m. The first semi-structured interview will be scheduled between Day 1 and prior to Month 1 visit. The end of study SSI will be scheduled within approximately within approximately 4 weeks of their Month 12 study visit.
- n. **Note:** Patient study participants with \geq Grade 1 LFTs at screening and or day 1 must be discussed with the Medical Monitor prior to initiation of LA dosing; continuation in the study or progression onto LA dosing may require additional evaluations, including labs drawn after a period of oral dosing with CAB + RPV.
- o. Follow Up Visit - Conduct ~4 weeks after the last dose of investigational product (IP) if not entering Long-Term Follow Up and only if the participant has ongoing AEs or lab abnormalities at the last on-study visit. May be conducted by telephone.

Table 4 Schedule of Assessments Table for Staff Study Participants

Procedures	Prior to Enrollment	Intervention Period (Month)										
		Day 1	1	2	3	4	5	6	7	8	9	12
Staff Study Participant Questionnaire		X ^a				X ^b						X ^b
Staff Study Participant Interviews (SSI)		X ^a				X ^b						X ^b
Staff Study Participant Monthly Facilitation Calls ^c		X	X	X	X	X	X	X	X	X	X	

- a. Questionnaire and interview should be conducted prior to the first patient receiving their first CAB + RPV LA injection at that site.
- b. Questionnaire and interview should be conducted within approximately 4 weeks of the targeted subject visit at each site for Month 4 and after at least 50% of patient study participant visits at Month 12.
- c. Facilitation calls will continue during the enrollment period until the last enrolled subject achieves their Month 6 study visit.

Table 5 Schedule of Activities Table for Patient Study Participants (Long Term Follow Up)^a

Procedures for Long-Term Follow Up ^a	Month 3	Month 6	Month 9	Month 12	WD	Notes
HIV Associated Conditions, AE and SAE Assessments, Con Meds	X	X	X	X	X	
Every effort should be made to enter participants into the Long-Term Follow Up if they withdraw from or discontinue the study after receiving at least one dose of CAB LA and / or RPV LA.
 
a. The start of the 52-week follow-up period begins the day of the last CAB LA and/or RPV LA dose.
 
b. A PK sample for storage should be collected in the event of virologic failure during the LTFU phase
 
c. Participants who get pregnant while in study will have additional PK samples for CAB and RPV obtained, see Appendix 8
 
d. FRP only. U=urine; pregnant participants who remain in the study do not need pregnancy testing during the study, for the duration of their pregnancy
 
e. FRP should continue to receive counselling on the need to use adequate contraception for the entirety of the Long-Term Follow-Up Period.
 
f. Investigators must discuss choice of HAART regimen and timing of initiation with the medical monitor before initiating

HIV-1 RNA	X	X	X	X	X	
CD4+ cell counts	X	X	X	X	X	
Plasma for Storage	X	X	X	X	X	
PK Sample for Storage ^{b,c}						
Clinical Chemistry and Hematology	X	X	X	X	X	
Pregnancy Testing ^d	U	U	U	U	U	
Urinalysis				X	X	
PT/PTT/INR				X	X	
Contraception Counselling ^e	X	X	X	X	X	
HAART Dispensation ^f	X	X	X	X	X	

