enrolled into the trial and subsequently withdrawn from the study, for any reason, may not be re-screened. Participants may be enrolled as soon as all eligibility requirements have been confirmed at the site. Patient study participants with an undetectable HIV-1 RNA (<50 c/mL) at Screen are eligible to enter this study. A single repeat viral load to determine eligibility may be allowed ONLY after consultation with the medical monitor. Should a participant be allowed a repeat, results of this repeat must be available prior to Day 1 of this study, therefore the time needed for scheduling the Day 1 visit, lab draws and lab analysis should be considered.

HIV-infected participants who meet all eligibility criteria will be switched at Day 1 from their pre-baseline regimen to an oral regimen for one month (CAB 30 mg + RPV 25 mg). Participants will return to the clinic, and if laboratory and clinical evaluations continue to support progression into the LA portion of the study, will take the last dose of their oral regimen (CAB 30 mg + RPV 25 mg), and receive the first CAB LA (600 mg) + RPV LA (900 mg) injections (within 2 hours of the final oral dose of CAB + RPV). All subsequent injections (CAB LA 400 mg + RPV LA 600 mg) will occur every month thereafter. Note: Patient study participants with \geq Grade 1 LFTs at screening and or day 1 must be discussed with the Medical Monitor prior to initiation of LA dosing; continuation in the study or progression onto LA dosing may require additional evaluations, including labs drawn after a period of oral dosing with CAB + RPV.

The dosing window for the second and third injection (Month 2 and Month 3) will be +0 / -7 days from the projected dosing visit; All subsequent injection windows (beginning at Month 4) will be +7/-7 days from the projected date of the visit. Doses outside of the window *may* be allowed with prior Medical Monitor approval.

Participants will continue CAB LA + RPV LA until:

- study intervention is locally approved and commercially available,
- the participant no longer derives clinical benefit,
- the participant meets a protocol-defined reason for discontinuation
- the development of either CAB LA or RPV LA is terminated
- participant withdraws consent
- investigator discretion
- participant or investigator non-compliance
- termination of the study by the Sponsor.

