6.2.1. Dosing Considerations for CAB LA + RPV LA

Vials of CAB LA and RPV LA are each supplied as a suspension and need no further dilution or reconstitution. Since RPV LA requires refrigeration, sites should allow the vial(s) to come to approximately room temperature prior to injecting. The vials should be gently inverted a few times to re-suspend sediments and allow bubbles to subside, and then use a syringe or provided vial adapter to withdraw the required volume of suspension for IM injection.

All injections must be given intramuscularly in the gluteus medius. Sites may use their discretion as to where in the gluteus muscle each injection is given according to individual participant circumstance. If possible, injections should be spaced approximately 2 cm from one another, from the site of any previous injection or any injection site reaction. The time and location of injection will be captured in the eCRF.

Intermuscular injections should be administered at a 90-degree angle into the gluteus medius muscle using a needle of appropriate gauge and length (In most participants, a 1.5” 23 gauge needle for CAB LA and a 1.5” 23 gauge needle for RPV LA is recommended). The needle should be long enough to reach the muscle mass and prevent study drug from seeping into subcutaneous tissue, but not so long as to involve underlying nerves, blood vessels, or bone. Variable needle lengths and/or needles with different gauge (CAB LA: 21 to 25 gauge; RPV LA: 21 to 23 gauge) are permitted if needed to accommodate individual body types. Longer needle lengths may be required for participants with higher body mass indexes (BMIs, example > 30), to ensure that injections are administered intramuscularly as opposed to subcutaneously. BMI, needle gauge and length used will be collected in the eCRF. Additional details of the injection device used by sites for IM administration including, but not limited to functional performance, may also be collected within the eCRF.

At the Day 1 visit, participants transitioning from oral CAB + RPV should be dosed with the IM regimen within 2 hours of taking the last oral regimen dose where possible.

Should IM maladministration be suspected at any time (e.g., suspected under or overdose or inadvertent IV dosing), the investigator may consider requesting the participant stay

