6.6.2. IM Dosing

Participants receiving CAB LA and/or RPV LA are anticipated to be at risk for development of virologic resistance if ART is interrupted. The time period during which participants are at risk for development of virologic resistance may be determined by the period between when drug levels fall below therapeutic values and when they fall below levels which exert selective pressure on HIV. This time period will vary by ART agent and is dependent upon effective concentration, inhibitory concentration, and half-life. Plasma concentrations of both LA drugs may be measurable for more than one year following IM injections. Any interruption in IM dosing should be discussed with the Medical Monitor. Investigators should ensure that the participant initiates alternative highly active ART to minimize the risk of developing resistance as concentrations of CAB and RPV decline over time.

IM dosing is expected to occur during the week in which the participant’s projected visit falls (as according to the date of the first injection).

Since the first injection visit (Month 1) will determine the future injection visit schedule for participants, planning for the first injection visit date (within allowed visit windows) should take into consideration the availability of the participants to adhere to future visit windows (planned vacations, business trips, *etc.*).

CAB LA + RPV LA dosing for participants transitioning from oral CAB + RPV is as follows:

All injections should be planned as single injections per drug.

6.6.2.1. IM injections every 1 month:

On Day 1, participants will return to the clinic, take the last dose of their oral (CAB 30 mg + RPV 25 mg), and receive the first CAB LA (600 mg) + RPV LA (900 mg) injections (within 2 hours of the final oral dose of CAB + RPV).

The second injection will be administered at Month 2 (CAB LA 400 mg + RPV LA 600 mg, with all subsequent injections (CAB LA 400 mg + RPV LA 600 mg) occurring every 1 month thereafter. The dosing window for the second and third injections allow administration between -7 days of the proposed injection visit date but preferably not later than the target date (-7 days/ +0 days around the proposed visit date). Beginning on Month 4, a dosing window (± 7 days) for injections is stipulated. The Medical Monitor must be contacted to discuss individual participant case management if a dose must be administered outside of the window.

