10.6. Appendix 6: Toxicity Management

10.6.1. Treatment Interruption Due to an Adverse Event

IP may be interrupted at the discretion of the Investigator and according to the severity of the AE. If one or more antiretroviral medications is held due to toxicity or adverse events, all antiretroviral medications must be held to reduce the risk of development of resistance taking into account both the length of the planned interruption and the pharmacokinetic half-life of each antiretroviral of the regimen, in a way to minimize the risk of development of resistance.

No toxicity-related dose reductions of IP will be allowed. IP should be restarted as soon as medically appropriate; in general, for oral dosing, this should be no longer than 14 days after discontinuation (unless Grade 3 or 4 toxicities persist). Any interruption in therapy during the Maintenance Phase, oral dosing, of greater than 7 consecutive days must be discussed with and agreed by the Medical Monitor prior to resumption of therapy. The Medical Monitor must be contacted upon becoming aware of resumption in therapy, if therapy was resumed without prior approval. **IM dosing is expected to occur during the week in which the participant's projected visit falls (as according to the date of the first injection visit [Month 1]). A +0 / -7 day window is stipulated around the projected dosing date for dosing injections at Month 2 and Month 3. A +7 / -7 day window, from the projected visit date, is allowable from the fourth injections forward for IM dosing but not preferred.** Any interruption outside of this guidance MUST be discussed with the Medical Monitor prior to reinitiating IM IP.

Guidance is provided below on general participant management and IP interruptions based on the severity of the AE. All changes in the IP regimen must be accurately recorded in the participant's eCRF.

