10.12.3. Permissible Use of Antiretroviral Therapy

In order to minimize the risk of gaps in HIV-1 antiretroviral therapy (ART) for participants impacted by COVID-19 in the clinical trial, the following options can be considered with regards to ART dosing, in order of preference:

1. Where possible, and safe to do, please continue to prioritize IM dosing visits in order to keep the participants on the protocol-defined regimen
 - a. Qualified healthcare professionals (HCPs) trained on study procedures can administer IM injections outside of the study clinic setting (e.g. home, nursing facility, hospital), assuming this can be done safely, without compromising investigational product preparation/handling/storage/accountability requirements and done in accordance with local requirements. Please seek approval by the study team on a case-by-case basis.

2. If a participant is not able to attend an IM injection visit due to COVID-19 related restrictions, the gap in IM dosing should be covered with oral ART, until IM dosing can resume. Participants should be reminded of the importance of adhering with daily oral dosing. Two options can be approved for oral bridging therapy in consultation with the Medical Monitor, listed in order of preference:
 - a. Oral CAB + RPV
 - i. Investigator should request availability of oral CAB + RPV supplies, prior to pursuing option b.
 - b. Oral standard of care (SOC) commercial ART (prescribed locally)

Oral bridging with CAB + RPV

The protocol permits oral bridging to cover planned missed injections with oral CAB + RPV, only until IM dosing can be resumed. The start date of oral bridging should be within the dosing window for the missed IM dosing visit. This recommendation can be used to accommodate requests for oral dosing due to COVID-19. Oral bridging recommendations should be followed as per protocol Section 6.6.1.1. The process and required information for requesting oral bridging can be found in your Study Reference/Procedure Manual. Please continue to reach out to your study medical monitor for approval of oral bridging, in order to document use and to ensure expeditious shipment of oral CAB + RPV to your site.

Participants who use oral CAB + RPV as short-term oral bridging are permitted to return to IM dosing, on protocol, once the COVID-19 conditions permit resumption of site activities.

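### Table 3 footnote k counts injection dates from Day 1, but Sections 6.6.2 and 10.6.1 count them from the first injection, so one dose can be both in and out of window

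*Protocol*

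**What the plan says.** Footnote k to Table 3 in Section 1.5 expects intramuscular dosing in the month in which the "projected visit falls (as according to the Day 1 visit" places it. It then sets -7/+0 days for Months 2 and 3 and ±7 days from Month 4.

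In this schedule Day 1 is not an injection visit. Section 1.3 says that eligible participants "will be switched at Day 1 from their pre-baseline regimen to an oral regimen for one month". Table 3 has oral dispensation in the Day 1 column and long-acting administration from Month 1. Footnote k itself puts the loading dose at Month 1, and the dosing table in Section 6.1 agrees.

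Section 6.6.2 uses a week rather than a month and a different anchor: "projected visit falls (as according to the date of the first injection". It also states the rule outright: "Since the first injection visit (Month 1) will determine the future injection visit schedule for participants". Section 10.6.1 repeats it: "projected visit falls (as according to the date of the first injection visit [Month 1". Both sections carry the same numerical windows as footnote k.

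Two further places use Day 1 for the first-injection visit. Section 6.6.2.1 has "On Day 1, participants will return to the clinic, take the last dose of their oral (CAB 30 mg + RPV 25 mg", and Section 6.2.1 has "At the Day 1 visit, participants transitioning from oral CAB + RPV should be dosed with the IM regimen".

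**The concern.** A window has no meaning without its reference date, and here the same window has two. A site working from the Schedule of Activities, to which Section 8 sends it for the exact timing of assessments, and a site working from Section 6.6.2 can classify the same injection differently.

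Three things depend on the classification:

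- **Medical Monitor contact.** Section 6.6.2.1 requires it when a dose has to be given outside the window.
- **Start of oral bridging under the COVID-19 appendix.** Section 10.12.3 says: "The start date of oral bridging should be within the dosing window for the missed IM dosing visit".
- **The secondary fidelity endpoint.** It counts injections given within a target window around the expected date (Sections 1.2 and 3).

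Months 2 and 3 are the sensitive visits, because no late days are allowed there.

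**Working it through.** The protocol offers no figure to reproduce, so the check is calendar arithmetic.

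**Inputs.** Anchor A (footnote k): Month m target = Day 1 + m months. Anchor B (Sections 6.6.2 and 10.6.1): Month m target = first injection + (m - 1) months. Windows: [-7, 0] at Months 2 and 3, which is 8 days; [-7, +7] from Month 4, which is 15 days. Let s be the number of days by which the first injection differs from Day 1 + 1 month. The protocol does not state s; ±7 days is assumed.

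**Can s differ from zero?** Yes. Section 6.6.2 tells sites to plan the first injection date around the participant's availability within visit windows, but the protocol gives no size for a Month 1 window. The lead-in is one month in Section 1.3 and 4 weeks in the risk table of Section 2.3.1. From Day 1 on 1 July, 28 days leads to 29 July against a one-month date of 1 August, so s = -3.

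**Disagreement.** Put the A target at 0 and the B target at s.

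- Months 2 and 3: the windows [-7, 0] and [s-7, s] share 8 - |s| days. Days in one window only: 8 + 8 - 2(8 - |s|) = 2|s|.
- From Month 4: the windows [-7, 7] and [s-7, s+7] share 15 - |s| days. Days in one window only: 15 + 15 - 2(15 - |s|) = 2|s|.

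| \|s\| | Days in one window only | Shared, Months 2-3 (of 8) | Shared, Month 4 on (of 15) |
|---|---|---|---|
| 0 | 0 | 8 | 15 |
| 1 | 2 | 7 | 14 |
| 3 | 6 | 5 | 12 |
| 5 | 10 | 3 | 10 |
| 7 | 14 | 1 | 8 |

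**Late first injection (s = +5).** Day 1 on 1 July, first injection on 6 August. The Month 2 target is 1 September under A and 6 September under B. An injection on 4 September is +3 days under A (out of window) and -2 days under B (in window).

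**Early first injection (s = -5).** First injection on 27 July. The last permitted Month 2 date is 1 September under A and 27 August under B. Measured from the loading dose, that is 36 days under A and 31 days under B.

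**Smallest late shift (s = +1).** A Month 2 or Month 3 dose given exactly on the B target is +1 day under A, so out of window. From Month 4 an on-target B dose stays inside the A window for every |s| up to 7.

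**The case against.** The best answer is that footnote k uses Day 1 as a loose label for the first injection. Sections 6.2.1 and 6.6.2.1 do so, and the notes to Figures 2 and 4 define it that way for the pharmacokinetic simulations. On that reading the anchors agree and only the terminology is careless. This may well explain how the wording arose. It does not rescue the text: footnote k sits under a table with its own Day 1 column for oral dispensation, and the footnote places the loading dose at Month 1.

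It can also be said that Section 6.6.2 states the governing rule, that Section 10.6.1 agrees, and that footnote k is the lone outlier. That is right, and it shows which way to correct.

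The size is conditional, and the larger shifts may be uncommon. The late example needs 37 daily oral doses (1 July to 6 August, both days counted), while tablets come in bottles of 30 and Table 3 shows dispensation at Day 1 only. The number of bottles dispensed is not stated, so s = +5 is not excluded. Nor does supply point to s = 0: from 1 July to 1 August is already 32 doses, and a single bottle ends on 30 July, which gives s = -2.

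Some consequences are softer than they first appear. The bridging rule says should, applies to COVID-19 disruption, and involves the Medical Monitor anyway. The expected injection date for the fidelity endpoint could be settled in the Reporting and Analysis Plan, which is not at hand. The Study Procedures Manual may give further dosing detail. None of these cures a contradictory dosing instruction in the protocol itself.

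**Conclusion.** The concern holds. As written, footnote k contradicts Sections 6.6.2 and 10.6.1 on the date from which injection windows are measured. The two readings disagree on 2|s| calendar days at each visit from Month 2, which is 2 to 14 days for an assumed shift of 1 to 7 days either way and none at s = 0.

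The practical effect is greatest at Months 2 and 3. A late first injection makes an on-time dose look late under footnote k. An early one lets the second dose run later than Section 6.6.2 allows without prompting contact with the Medical Monitor. No participant harm is shown, and how often s differs from zero cannot be known from the protocol. It should be fixed because it is operative dosing text in the schedule that sites follow.

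**What to change.** In Table 3 footnote k, replace the Day 1 anchor with the one in Section 10.6.1 ("projected visit falls (as according to the date of the first injection visit [Month 1") and change month to week so that it matches Sections 6.6.2 and 10.6.1. In Sections 6.2.1 and 6.6.2.1, change Day 1 to Month 1 where the first-injection visit is meant. Let the expected injection date in the fidelity endpoint follow the same anchor.

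With one anchor, every injection has a single window status for any s. The cost is three wording corrections; the windows, visits and data collected stay as they are.
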